Power, sample size, and detectable effects. All of the power calculations were conducted with PASS12.³¹ The primary objective of the analysis is to estimate the effect of the PILI DPP-LI relative to the effect of the WORD DPP-LI with respect to the percentage of weight loss from pre- to post-intervention. Based on prior PILI DPP-LI research,²¹ it is hypothesized that the adapted intervention will result in 2.5kg weight loss (SD=7) larger than the WORD DPP-LI (this is ~4% body weight loss), which reflects a medium effect size of 0.36.³² Using the randomized clustered design, it is estimated that a sample size of 32 churches (16 clusters per arm with 12 individuals per cluster) would total N=384. This achieves 91% power to detect a difference of 2.5kg between the group means when the standard deviation is 7 (ES=0.35) and the intra-cluster correlation is 0.01 using a two-sided *t*-test with a significance level of 0.05, or 80% to detect smaller effects (ES=0.31) if observed. It is planned to impute missing data (see below), therefore all randomized participants will be included in the analysis according to an intention-to-treat protocol.

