assessment. Measures of weight will be obtained at multiple points during the study (pre-intervention, post-intervention, and 12-months post-intervention), and both post-intervention and 12-months (six months post-initiation) will be modeled, but in separate models. General linear and mixed ANCOVA regression models for continuous measures with clustering will be utilized, with treatment effect estimated as the distance between the fitted group-specific means at the post-intervention assessment, while adjusting for the fitted distance between them at baseline, conservatively. In addition, an adjustment will be made within the model for demographic factors and other covariates listed above. In order to model the outcome at the 12-month time point, a similar model to the one described above will be applied with repeated measures, and incorporate intervention, time, and their interaction effect, while adjusting for the same covariates as in the first model. This will allow examination and test weight change trajectories over time for both groups. Secondary outcome measures that are continuous in nature, such as HbA1c, will also be modeled using the same approach used to test the primary outcome (a general linear mixed model). Secondary outcomes that are discrete will be modeled using logistic regression or generalized estimating equations (GEE) for repeated binary measures accounting for the correlation within groups.

Additional analysis will be done to: 1) determine if aspects of participants' built environment as measured by Google StreetView influence effectiveness of the project's intervention, 2) determine if aspects of the food environment based on Business Analyst in ArcGIS influence effectiveness of the project's intervention.

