Sensitivity analyses to determine the impact of key assumptions. We will examine the distributional assumptions for our outcome measures, which may prompt transformations if justified. We will also compare the results of parametric and non-parametric univariate tests (for instance Wilcoxon test, Kolmogorov-Smirnov test, or Fisher's Exact test, respectively) as a sensitivity step to confirm the inferences. In a case where distributional assumptions are not met, non-parametric tests will be applied. While we will track and analyze the effect of dosage (number of sessions completed), we will use an intention-to-treat analysis. To account for missing data we will compare imputation methods under several assumed missing data mechanisms, missing completely at random (MCAR), missing at random (MAR), and missing not at random (MNAR), in order to determine which underlying mechanism best fits our data.

Plans to address missing data. The study team will minimize missing data by using highly qualified staff to systematically collect data from all participants. Furthermore, we will use REDCap to monitor the occurrence of missing data during field collection. REDCap has a standard missing data report to facilitate the identification of missing data fields, which allows for continuous data quality monitoring so that missing data can be immediately collected. If a participant drops out, the study team will document why the drop out occurred. The study team will continue to collect information on all outcomes from participants, unless consent is withdrawn. Given recent advances in handling missing data in longitudinal studies, we have several reasonable approaches that we will apply and compare. We will compare the results of the analysis using three approaches as a comprehensive sensitivity check: 1) use a random effects model in SAS PROC MIXED (or weighted GEE for discrete outcomes) that makes use of all available data when assuming observations are missing completely at random (MCAR); 2)

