perform multiple imputations (N=25) in SAS PROC MI when assuming observations are missing at random (MAR); and 3) perform pattern-mixture model imputations in SAS PROC MI when assuming observations are missing not at random (MNAR). To address this potential source of inferential error, we will use monotone regression-based, multiple random imputations of the outcomes. These imputations will help minimize loss of power resulting from attrition. We will use demographic covariates and prior weight measurements that are available in this predictive model. The analysis will then be carried out in multiple data sets, and the results combined using standard methods in SAS PROC MIANALYZE to produce summary effect and standard error estimates that incorporate the imputation error.³³⁻³⁴

Plans to address heterogeneity of treatment effect. Potential differential effects of the PILI DPP-LI among subgroups will be evaluated to determine its effectiveness in specific population segments. This will be done by testing two-way interactions between intervention assignment and covariates of interest. These include sex, age, education, insurance status, and marital status. Bonferroni correction will be applied to control p-values for multiple comparisons. For these exploratory comparisons, we will report all relevant subgroup outcomes analyzed.

Ethical Considerations. This study will be conducted in accordance with all applicable government regulations and University of Arkansas for Medical Sciences research policies and procedures. This protocol and any amendments will be submitted and approved by the UAMS Institutional Review Board (IRB) to conduct the study.

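### As written, the imputation predictor list leaves out the pre-intervention value of HbA1c and every other secondary outcome, although it is collected and the analysis model adjusts for it

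*Combined protocol and SAP*

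**What the plan says.** All references are to the Combined protocol and SAP.

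- **Plans to address missing data.** Three approaches will be compared: a random effects model on all available data ("weighted GEE for discrete outcomes"), 25 multiple imputations under missing at random, and pattern-mixture imputation under missing not at random. Then: "we will use monotone regression-based, multiple random imputations of the outcomes". The only statement of predictors is "We will use demographic covariates and prior weight measurements that are available in this predictive model". No separate imputation model is given for any secondary outcome.
- **Statistical analysis plan.** The model for weight adjusts for baseline. Continuous secondary outcomes, "such as HbA1c, will also be modeled using the same approach used to test the primary outcome".
- **Power, sample size, and detectable effects.** Imputation carries the intention-to-treat analysis: "It is planned to impute missing data (see below), therefore all randomized participants will be included in the analysis".
- **Data collection, Biometric Data and Survey Data.** HbA1c, waist, blood pressure and the survey scales are all measured before the intervention.

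**The concern.** An imputation model should contain at least the variables in the analysis model that will use the imputed data. For weight, the list supplies the key variable. For HbA1c it does not. The analysis conditions on baseline HbA1c, while a missing follow-up value would be drawn from demographics and weight. A participant with high baseline HbA1c who is lost would be imputed towards the average, as though HbA1c had fallen.

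Two consequences follow. The baseline slope is flattened and the residual variance raised, so imputation can give a wider standard error than dropping the missing participants, although the SAP expects it to limit the power lost to attrition. And if participants with particular baseline values are lost more in one arm than in the other, the PILI-WORD difference in the outcome is shifted.

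**Working it through.** **1. The plan's own figure.** The documents give no figure for imputing secondary outcomes. The stated power for weight (16 churches per arm, 12 people each, 2.5 kg, SD 7, ICC 0.01, two-sided 0.05) reproduces:

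- Design effect = 1 + (12 − 1) × 0.01 = 1.11; effective n per arm = 192 / 1.11 = 173.0.
- SE = 7 × √(2 / 173.0) = 0.753; 2.5 / 0.753 = 3.32; power = Φ(3.32 − 1.96) = 91.3%, against 91% stated.

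So N = 384 is used below.

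**2. Assumptions (not in the documents).** Outcome standardised to SD 1; baseline-to-follow-up correlation ρ from 0.3 to 0.85; fraction missing m from 10% to 30%. Arm is included in the imputation model, to isolate the effect of omitting baseline.

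**3. Standard error by hand, values missing completely at random.** Treat demographics and weight as weak predictors and ignore the small ICC.

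- Complete-case variance = 4(1 − ρ²) / [N(1 − m)].
- With baseline omitted, the slope in the filled-in data falls to about (1 − m)ρ. Within-imputation variance = 4[1 − (1 − m)²ρ²] / N.
- Between-imputation variance B = 4m/N + 4m² / [N(1 − m)].
- Pooled variance = within + (1 + 1/25) × B.

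For ρ = 0.85, m = 0.20:

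- Complete case: 4 × 0.2775 / 307.2 = 0.003613; SE 0.0601.
- Within: slope 0.8 × 0.85 = 0.68; 4 × (1 − 0.4624) / 384 = 0.00560.
- B = 0.002083 + 0.000521 = 0.002604.
- Pooled: 0.00560 + 1.04 × 0.002604 = 0.008308; SE 0.0912.
- Ratio = 0.0912 / 0.0601 = 1.52.

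**4. Simulation.** 250-400 trials per scenario, 32 clusters of 12, ICC 0.01, 25 imputations, Rubin's rules, and baseline-adjusted least squares as a simplified ANCOVA. Weight and one demographic variable were each assumed to correlate 0.2 with the baseline outcome. Ratio of pooled SE to complete-case SE:

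| ρ | 10% missing | 20% missing | 30% missing | By hand, 20% |
|---|---|---|---|---|
| 0.3 | 1.02 | 1.03 | 1.04 | 1.03 |
| 0.5 | 1.05 | 1.08 | 1.11 | 1.08 |
| 0.7 | 1.12 | 1.20 | 1.27 | 1.22 |
| 0.85 | 1.30 | 1.50 | 1.62 | 1.52 |

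The actual spread of the estimates rises less. At ρ = 0.85 and 20% missing it was 0.0785 against 0.0639 (ratio 1.23), and in a second simulation on the HbA1c scale 0.109 against 0.085 (1.28). With own baseline added, the pooled SE ratio is 1.00-1.01 throughout.

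**5. Bias in the between-arm difference.** If the lost participants in an arm have a mean baseline g SDs above those retained, the imputed arm mean is wrong by about −m × ρ × SD × g. The error in the difference is the gap between the two arms' values of this term, and it cancels when m and g are equal across arms.

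- *Equal loss rate and equal dependence* (log-odds 1 per SD, nominal 20% missing): bias −0.005, −0.007 and −0.002 SD at ρ = 0.5, 0.7 and 0.85, i.e. none. Overall mean change is still biased, by −0.09, −0.14 and −0.16 SD.
- *Equal dependence, unequal loss* (HbA1c SD 1.5, true difference −0.30, ρ = 0.85, about 25% against 15% lost, log-odds 0.7 per SD): g is about 0.65, so by hand 0.85 × 1.5 × 0.65 × (0.25 − 0.15) = 0.08. Simulation gave −0.36 to −0.38 in one direction and −0.22 to −0.23 in the other. With own baseline included it gave −0.30.
- *Dependence in one arm only* (true effect 0.30 SD, ρ = 0.5, 0.7, 0.85): bias −0.10, −0.12, −0.16 SD. *Opposite dependence by arm*, an extreme case: −0.18, −0.27, −0.32 SD.

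Baseline-adjusted complete cases, and imputation with own baseline, were unbiased for the between-arm difference in all of these, within Monte Carlo error (about 0.013 SD).

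**The case against.** **The list may describe weight only.** It does not say that nothing else will be used, earlier weight is the lagged value of the one powered outcome, and the SAP carries the primary approach over to HbA1c. This reading is possible. But the imputation sentence refers to outcomes in the plural, the same section provides for discrete outcomes, and no other imputation model appears. If weight alone was meant, HbA1c has no specified imputation model and the same sentence is still needed.

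**Not every analysis imputes.** A reader might infer that every missing outcome is filled in this way. The documents do not support that: the first of the three approaches uses all available data without imputation, so an HbA1c result free of this problem is already planned. It does not repair the other results, and a disagreement between approaches could then reflect the predictor list and be misread as evidence about the missing-data mechanism.

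**Bias is conditional.** A reader might infer that the arm comparison is biased whenever loss depends on baseline. It is not, if loss rate and dependence are equal across arms and arm is in the imputation model. Unequal loss is plausible, because the two curricula differ in number, timing and content of modules, but the documents give no loss data.

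**The large figure is a high-correlation case.** The 50% needs ρ = 0.85. For blood pressure or survey scores ρ may be much lower. The demographic form also records health status and some co-morbidities. If a diabetes indicator is among them (38.4% prevalence from the pilot screening, assumed correlation 0.6-0.75 with baseline HbA1c), a 48% inflation on the HbA1c scale falls to roughly 36%-26%. The documents do not say which co-morbidities are recorded. This reduces the inflation without removing it.

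**The list also omits arm and church.** This stands. Taken literally, leaving out arm shrinks every imputed effect, weight included, by about the fraction missing: on a true 0.30 SD, 0.03, 0.06 and 0.09 at 10%, 20% and 30%. The estimates are then no more variable than complete-case (spread ratio 0.74-1.00), because they are pulled towards zero. It is a separate gap, which the same replacement sentence closes.

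**Conclusion.** The point holds for secondary outcomes in the imputation-based approaches: the missing-at-random imputation and, if it uses the same list, the pattern-mixture imputation. These matter because the power section rests the intention-to-treat analysis on imputation. The mixed model and weighted GEE on all available data are unaffected, and weight is unaffected by this particular omission.

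The precision cost at 20% missing is about 2-3% at ρ = 0.3, 8-9% at 0.5, 20% at 0.7 and 50% at 0.85 in pooled standard error; at 0.85 the real spread of estimates rises by about 20-30%. All of this assumes arm is in the imputation model, and correlation and loss rate are assumptions throughout. Bias in the PILI-WORD difference requires loss that depends on the baseline value together with a loss rate or dependence that differs by arm. The text should be corrected before analysis. It does not threaten the primary result by this route.

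**What to change.** In Plans to address missing data, replace the predictor sentence with:

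> The imputation model for each outcome includes intervention arm, that outcome's own pre-intervention value and its other measured visits, weight measurements, demographic covariates, and every other variable in that outcome's analysis model, with the church/group clustering reflected; binary outcomes are imputed with a logistic model.

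State whether the pattern-mixture imputation uses the same predictors. The cost is this wording and a few extra variables in PROC MI, all already collected. No change to data collection, sample size or the analysis models is needed.

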Specific Aim. Our aim is to compare the effectiveness of achieving weight loss between two Diabetes Prevention Program Lifestyle Interventions (DPP-LI), the WORD DPP-LI¹⁸⁻²⁰ and a culturally-adapted PILI DPP-LI²¹⁻²², in the Marshallese population using a randomized controlled trial (RCT) with a goal of 378 participants.

Study design. The study design is a comparative effectiveness research (CER), RCT conducted in church settings or other community setting convenient to the participant group with the Marshallese population. Churches were selected as the primary setting based on stakeholder input.

Randomized participant assignment. Randomization will occur at the church cluster level, with 1:1 assignment of churches to each arm. In churches with more than one group (i.e., churches with more than 20 participants, necessitating more than one group within those churches), all groups within an individual church will be randomized to the same arm. Community location based participant groups will be treated the same as if they were a church based group in the randomization process. Randomization will be conducted by a biostatistician or designated investigator, who will have no interactions with potential participants and has no supervisory role with study staff responsible for recruiting, consent, and intervention process.

Churches and community based participant groups will be blocked (i.e., grouped into similar units) according to geographic region and approximate number of adult church members. Using

a computer generated algorithm for random assignment, equal numbers of churches within each block will be assigned to the WORD DPP-LI arm and the PILI DPP-LI arm of the study.

Recruitment and Consent

Participants will be recruited through churches from Arkansas, Kansas, Missouri, and Oklahoma. The recruitment will also occur through clinics serving the Marshallese community and through local media targeting the Marshallese community. The recruitment goal is up to 400 participants through the duration of the study.

During recruitment, Marshallese study staff will give presentations and distribute study information in English and Marshallese within local community churches and meeting places. Those who express interest will complete an eligibility screener, to determine eligibility– see Inclusion/Exclusion criteria. The eligibility screener will include systolic and diastolic blood pressure and height and weight measurements to calculate BMI.

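### Pooling the 25 imputations without a complete-data df ignores that only about 32 churches are randomised; run that way, intervals are slightly too narrow

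*Combined protocol and SAP*

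**What the plan says.** All references are to the combined protocol and SAP.

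- **Randomised unit.** Under Randomized participant assignment: "Randomization will occur at the church cluster level, with 1:1 assignment of churches to each arm". Churches are blocked by region and size, and "equal numbers of churches within each block will be assigned to the WORD DPP-LI arm and the PILI DPP-LI arm". The number of blocks is not given. Community groups enter randomisation as if they were churches.
- **Number of clusters.** Under Power, sample size, and detectable effects: "it is estimated that a sample size of 32 churches (16 clusters per arm with 12 individuals per cluster) would total N=384". The ICC is taken as 0.01 and the test as a two-sided t-test at 0.05.
- **Analysis model.** The Statistical analysis plan section handles clustering by a compound-symmetry covariance. It names no denominator df method.
- **Imputation and pooling.** Plans to address missing data will "perform multiple imputations (N=25) in SAS PROC MI" under MAR, adds pattern-mixture imputation under MNAR, and has the "results combined using standard methods in SAS PROC MIANALYZE to produce summary effect and standard error estimates". It mentions neither a complete-data df nor a small-sample adjustment.
- **Role of imputation.** The power section gives imputation as the reason all randomised participants enter the intention-to-treat analysis. Plans to address missing data lists it as one of three approaches compared as a sensitivity check, beside an all-available-data random effects model in PROC MIXED.

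**The concern.** The unadjusted combining rule takes its df only from the number of imputations and the share of variance due to missing data. It treats the complete-data analysis as having unlimited df. Here that analysis compares churches, and even with no missing data it has 30 df at most. The fewer the missing data, the larger the pooled df becomes, and the further it moves from what the design supports. The test is then referred to something close to a normal distribution, so the interval is short and a nominal 5% test can reject too often. Nothing written elsewhere in the plan restores the limit, because the mixed model's denominator df is not stated either.

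**Working it through.** **Inputs from the documents.** 32 churches, 16 per arm, 12 people each (N = 384); difference 2.5 kg; SD 7; ICC 0.01; two-sided 0.05; m = 25 imputations.

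**Assumption.** No dropout rate or fraction of missing information is given. Let λ be the between-imputation share of total variance, (1 + 1/m)B/T, taken as 10%, 20% and 30%.

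**1. The plan's own power figure.** Design effect = 1 + 11 × 0.01 = 1.11. SE = 7 × √(2 × 1.11/192) = 0.753 kg. Power for 2.5 kg is 91.3% (normal), 91.2% (t, 382 df) or 89.5% (t, 30 df). The stated 91% is reproduced to within two points under each, so it does not show which df was used. The second statement, "or 80% to detect smaller effects (ES=0.31) if observed", fits 30 df a little better: the effect size detectable with 80% power is 0.311 on 30 df and 0.302 on 382 df. That is suggestive only.

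**2. Between-church df.** 32 − 2 = 30, and fewer if block or other church-level terms are fitted.

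**3. Pooled df and critical values.**

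- Unadjusted: ν = (m − 1)/λ² = 24/λ².
- Small-sample (Barnard-Rubin) with complete-data df 30: ν_obs = (1 − λ) × 30 × 31/33, and ν* = 1/(1/ν + 1/ν_obs).

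Worked at λ = 0.20: ν = 24/0.04 = 600; ν_obs = 0.8 × 28.18 = 22.55; ν* = 1/(1/600 + 1/22.55) = 21.7.

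| λ | ν unadjusted | critical value | ν* | critical value | small-sample interval wider by |
|---|---|---|---|---|---|
| 0.10 | 2,400 | 1.961 | 25.1 | 2.059 | 5.0% |
| 0.20 | 600 | 1.964 | 21.7 | 2.075 | 5.7% |
| 0.30 | 267 | 1.969 | 18.4 | 2.098 | 6.6% |

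Even at λ = 0.50 the unadjusted rule gives 96 df, against 12.3.

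With no missing data, SE 0.753 kg gives a 95% half-width of 1.475 kg using the normal value and 1.537 kg using t on 30 df (2.042).

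**4. Type I error.** Idealised simulation: within-imputation variance on 30 df, between-imputation variance on 24 df, standard error otherwise correct. This matches an unconstrained compound-symmetry fit.

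| λ | unadjusted df | Barnard-Rubin df |
|---|---|---|
| 0.10 | 5.7–5.8% | 4.6–4.7% |
| 0.20 | 5.6% | 4.3–4.4% |
| 0.30 | 5.4–5.5% | 4.1% |

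Ranges are from repeated runs of at least 1,000,000 draws.

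**5. Dependence on how church variance is fitted.** Simulation of 32 churches of 12 with no missing data, using critical values 1.961 to 1.969. Unconstrained compound symmetry rejects in 5.8–5.9% of trials. With a random intercept whose variance cannot go below zero, the church variance is estimated as zero in about 37% of trials at ICC 0.01, and rejection is 4.8–4.9%. At ICC 0.02 it is 5.2–5.3%. The ICC of 0.02 is a sensitivity value of this check, not a figure from the plan.

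**The case against.** Four points can be made for the plan.

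- **The wording does not rule out the right df.** The pooling sentence names a procedure and gives no formula or reference distribution. Supplying a complete-data df in that same procedure would be consistent with it. This stands: a reader might infer that the primary interval is certainly too narrow, and the documents do not support that. What they show is a named method without the input it needs here.
- **Imputation may not be primary.** If the all-available-data mixed model is the primary analysis, no pooling touches the main result. This stands in part. The plan's two descriptions of imputation's role differ, and the power section's points to the intention-to-treat analysis. The denominator df would still be unstated for the mixed model.
- **The inflation may not occur at the planned ICC.** With church variance constrained to be non-negative, rejection at ICC 0.01 is about 4.8–4.9%. This also stands. The Statistical analysis plan section names compound symmetry, but the missing-data section names a random effects model, and nothing says how negative estimates are handled.
- **The remedy is not free.** It makes intervals 5% to 7% wider and the test somewhat conservative. That is correct and is a cost to be stated.

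One could also add the effect of leaving church out of the listed imputation predictors and arrive at a larger error rate. That is a separate question, and a markedly larger figure would need an ICC above the only one the documents give.

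**Conclusion.** The concern holds in a limited form. If the imputations are pooled as described, with no complete-data df, the pooled df is in the hundreds or thousands where the design supports at most 30. The small-sample interval would be about 5% to 7% wider, and under compound symmetry the two-sided type I error of the unadjusted rule is about 5.4% to 5.8%. This is an excess of under one percentage point, and it could vanish at ICC 0.01 with a non-negative church variance.

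The conclusion rests on three assumptions: missing information of 10% to 30%, 32 churches actually randomised, and a standard error that is otherwise correct. It bears on the primary result only if imputation is the primary intention-to-treat analysis. The effect is modest, but the df rule sets the test threshold, so it should be fixed before the data are seen.

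**What to change.** Add to Plans to address missing data:

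1. Imputed results are pooled with Barnard-Rubin small-sample df. The complete-data df (the EDF option) is the realised number of randomised clusters minus 2, less any block or cluster-level terms fitted. Write it as this rule and not as a fixed 30, because 32 churches is a planning figure and the number of blocks is not stated.
2. The same rule applies to every other imputed continuous outcome.

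Add to the Statistical analysis plan section:

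3. The mixed model uses the matching between-cluster denominator df, with a statement of whether the church variance or covariance may be negative.
4. Which analysis is primary, multiple imputation or the all-available-data model, and which are sensitivity analyses.

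The cost is one option in the pooling step and a few sentences, with no extra participants or data. Intervals become about 5% to 7% wider than under unadjusted pooling, and the test is slightly conservative (about 4.1% to 4.6% at 10% to 30% missing information).
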